6. TIME SCHEDULE

Outcome / Time point	Baseline Consultation prior to inclusion	Diagnostic RF treatment	RF treatment	Consultation 6 weeks post treatment	Telephonic contact
Age	X				
Sex	X				
Duration of symptoms	X				
Previous knee surgery	X				
Referring physician	X				
Indication for treatment	X				
NRS	X			X	X
Strong opioid use	X			X	X
Chronic widespread pain	X				
NRS reduction $\geq 50\%$		X		X	X
Treating physician			X		
Subjective physical functioning score					X
GPE $\geq 50\%$				X	X
Adverse events				X	X
Informed consent					X

7. STATISTICAL CONSIDERATIONS

Data will be presented as mean values and standard deviations or as median values and interquartile range (IQR) depending on the distribution of the data. The average post-treatment pain score will be estimated using linear mixed effects regression analysis using time since treatment as independent variable. We will use this multilevel approach as (most) patients contribute more than one post-treatment pain score to the dataset. This way, we will be able to estimate the 3 and 6 months effect of RF treatment. The statistical analysis will be performed using SPSS.

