2. STUDY DESIGN

2.1 Study design

This study is designed as a retrospective longitudinal cohort study of patients treated with a radiofrequency treatment of the genicular nerves in a single-center (ZOL, Genk) between 1 September 2017 and 30 June 2020. Each knee will be considered as a unique observation, and bilateral procedures were assessed specific to each knee treated. Data retrieved from the patient files will be collected at baseline, 6 weeks post-intervention and telephonically at a third time point which ranges from 6 weeks to 3 years after the procedure. The following demographic and clinical data will be collected at baseline: patient age, sex, NRS score, length of symptom duration, indication for the procedure, use of strong opioids, history of previous knee surgery and the referring physician. Strong opioid analgesics are defined as all opioids excluding tramadol and codeine.

Data collected at 6 weeks post-intervention will include: NRS, GPE, adverse events, and concomitant use of strong opioids.

Patient's data will be collected at a third time point. Written informed consent will be obtained by mail prior to contact by phone. After receiving informed consent, patients will be contacted by telephone and data will be gathered on the same variables as at 6 weeks post-intervention and on subjective functional outcome.

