3. STUDY SETTING AND POPULATION

3.1 Study setting

The enrollment period will be between 1 September 2017 and 30 June 2020. The patients recruited were treated in an outpatient setting in the multidisciplinary chronic pain center in Lanaken, Campus St. Barbara, ZOL. Patients with chronic knee pain who qualify for a conventional radiofrequency treatment of the genicular nerves were recruited. Prior a diagnostic block was performed and in case of positive results patients were treated with conventional radiofrequency ablation. Follow up in the pain clinic consisted of a minimum of one consultation after treatment at six weeks post procedure. Further follow up was planned according to the needs of the patient at the pain clinic, orthopedist or general practitioner.

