4. STUDY OBJECTIVES

4.1 **The primary objective** of this study is to evaluate the treatment success of the conventional radiofrequency treatment of the genicular nerves in patients on patients diagnosed with chronic knee pain due to osteoarthritis of the knee or PPSP at six weeks post treatment. Treatment success is defined as a global perceived effect of at least 50% at measurement time point compared to baseline.

4.2 **The secondary objectives** are:

- Evaluation of treatment effect at a third time point at the end of the inclusion period
- Subgroup analysis of treatment success based on indication to treatment
- Evaluation of subjective functional improvement
- Evaluation of change in analgesics
- Estimation of the duration of effect of the treatment
- Adverse event

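### The mixed model's only predictor is time since treatment, which at the phone call nearly mirrors treatment date, so any drift over 2017–2020 leaks partly into the NRS time course

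*Combined protocol and SAP*

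**What the plan says.** Section 7 estimates the average post-treatment pain score by a linear mixed model "using time since treatment as independent variable". No treatment date, baseline NRS, indication or operator term is named. The multilevel form is justified "as (most) patients contribute more than one post-treatment pain score to the dataset", and the intended output is that "we will be able to estimate the 3 and 6 months effect of RF treatment".

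Three other sections fix when the scores are taken:

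- Section 2.1 includes procedures performed "between 1 September 2017 and 30 June 2020". It collects later data "telephonically at a third time point which ranges from 6 weeks to 3 years after the procedure".
- Section 4.2 places that contact in one period: "Evaluation of treatment effect at a third time point at the end of the inclusion period".
- Section 3.1 gives the common earlier visit: "Follow up in the pain clinic consisted of a minimum of one consultation after treatment at six weeks post procedure".

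The Section 6 time schedule records indication and treating physician, but Section 7 does not place either in the model. Indication is addressed only by a subgroup analysis of treatment success (Section 4.2).

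**The concern.** When everyone is called in the same period, time since treatment at the call is the call date minus the treatment date. A knee with three years of follow-up was treated in 2017, and one with a few weeks was treated in mid-2020. Section 1 describes the technique as novel and the indications are mixed, so operator experience or patient selection could have changed over those years. A model that knows only time since treatment must put part of any such change into its time effect.

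At stake is the NRS time course, a secondary result. If later-treated knees did better, the curve shows waning that did not happen. If they did worse, real waning is masked. In both cases the interval around the slope covers less often than stated.

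**Working it through.** **1. The plan's own follow-up range.** From 1 September 2017 to 30 June 2020 is 1,033 days, which is M = 33.9 months or 2.83 years. A single call date six weeks after the last treatment is 11 August 2020. The first-treated knee then has 1,033 + 42 = 1,075 days, or 2.94 years. This reproduces the stated range of 6 weeks to 3 years. The correlation between follow-up at the call and treatment date is −1.00 for one call date, −0.996 for a 3-month call window and −0.985 for a 6-month window.

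**2. Share of drift that reaches the slope.** The documents give no sample size, SD, within-knee correlation or drift, so these are assumptions. Section 7 also leaves open the random-effects structure and the coding of time. I take a random intercept per knee, linear time, one score at week 6 and one at the call, treatment dates uniform over M, no true waning, and NRS improving by D points from first to last treated.

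Let s be the gap between a knee's two scores, uniform on 0 to M.

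- Within knees the drift cancels, so the slope is 0. The information per knee is (M²/3)/(2σe²).
- Between knees, the mean score moves by D/M per unit of s and the mean time by 1/2, so the slope is 2D/M. The information per knee is (M²/48)/(σb² + σe²/2).
- The ratio of between to within information is k = 0.25 × (1 − ICC)/(1 + ICC).
- The share of D appearing as a time effect over M is 2k/(1 + k).

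| ICC | k | Share, complete pairs | Share, 30% without week 6 |
|---|---|---|---|
| 0.3 | 0.135 | 24% | 31% |
| 0.5 | 0.083 | 15% | 22% |
| 0.7 | 0.044 | 8% | 13% |

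The last column is from generalised least squares on the same design. A Monte Carlo check (150 knees, SD 2.5, ICC 0.5, D = 1, 200 runs) gave 13% with a simulation error of 2.4 points. With call scores alone the share is 100%.

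**3. Size on the NRS scale, 150 knees.** Slope bias per year = share × D / 2.83.

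- Between/within SD 1.8/1.6 (ICC 0.56), D = 1.0: 0.132 × 1.0 / 2.83 = 0.047. Simulation gave 0.045, with SE 0.108.
- SD 1.3/2.0 (ICC 0.30), D = 1.5: 0.239 × 1.5 / 2.83 = 0.127. Simulation gave 0.122, with SE 0.132.

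The simulated bias/SE ratios are 0.045/0.108 = 0.42 and 0.122/0.132 = 0.92. With coverage Φ(1.96 − δ) − Φ(−1.96 − δ), these give about 93% and 85%. The closed-form bias in the second case gives about 84%.

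**4. The 3- and 6-month means.** With linear time, D = 1 and ICC 0.5, they shift by −0.03 and −0.02. At ICC 0.3 and D = 1.5 the shifts are 1.5 × −0.048 = −0.07 and 1.5 × −0.027 = −0.04.

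If time is categorical, the 3- and 6-month call scores come only from knees treated around May and February 2020. For D = 1 and ICC 0.5 the shifts are then about −0.22 and −0.17. The spread from the shortest to the longest call category is 61%, 43% and 26% of D at ICC 0.3, 0.5 and 0.7.

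**5. With treatment date in the model.** The week-6 scores compare early and late knees at the same elapsed time, so they identify the date effect. The false slope falls to 0.000 of D in every calculated scenario (Monte Carlo −0.02, simulation error 0.02). With complete pairs the SE rises by the factor √(1 + k): 1.065, 1.041 and 1.022 at ICC 0.3, 0.5 and 0.7. In the two settings of step 3 the closed form gives 1.066 and 1.035. With 30% lacking week 6 and ICC 0.3 it is 1.109.

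**The case against.** The strongest reply is that the outputs Section 7 names, the 3- and 6-month effects, barely move under linear time, and that the patient-level term already draws on the week-6 scores. Both points stand for linear time and complete pairs. Section 7 does not commit to linear time, however, and its own wording concedes that not every patient has two scores.

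It is also fair to say that the drift is hypothetical. Nothing in the documents shows that results changed over the years, and 1.0 to 1.5 points is an assumption. The 84–85% coverage combines the larger drift with the lower within-knee correlation of the two settings; the milder setting is close to nominal.

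A reader might infer more than the documents support:

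- **That all of the drift is reported as waning.** This would hold only if the call scores were analysed alone. The planned model passes on a part, and the sign depends on the direction of the drift.
- **That the duration-of-effect result is distorted.** Section 5.2 defines duration by GPE, and Section 2.2 has the caller ask directly how long the treatment worked. Nothing derives it from the NRS model.
- **That the week-6 scores remove drift of every kind.** They remove drift that shifts week-6 and later scores equally. A change over the years in how long the effect lasts cannot be separated with these data, nor can a calendar effect at the call period.

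**Conclusion.** The point holds as a partial, direction-dependent leak into a secondary analysis. With time since treatment as the only predictor and one call period, about 8–24% of any drift by treatment date enters the NRS slope, given linear time, complete pairs and ICC 0.7 to 0.3. At the assumed drifts of 1.0 and 1.5 points and 150 knees, that is roughly 0.05 to 0.12 NRS per year. Leakage is larger with categorical time or missing week-6 scores.

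The structure of the problem is in the documents; the existence, size and sign of any drift are not. The calculations therefore do not show that waning will be falsely reported. The primary week-6 proportion is untouched. The change is worth making because it is cheap and can be specified before analysis.

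**What to change.** In Section 7, add treatment date (in months) and baseline NRS as fixed covariates in the mixed model, and report the post-treatment time course at the mean of both. State that waning is judged from the change after week 6 within knees, not by comparing early- with late-treated knees at the call.

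State the assumption as well: the treatment-date effect is taken to be the same at week 6 and later, and a change over the years in the durability of the effect cannot be distinguished.

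Baseline NRS is already collected, and treatment date is needed to compute time since treatment, so no new data are required. The price is a standard error of the time slope about 3–7% larger with complete pairs, and up to about 11% larger if 30% lack a week-6 score. These figures are for adding treatment date; the effect of adding baseline NRS was not calculated.

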8. INFORMED CONSENT

Patients in accordance with eligibility criteria will be contacted by mail to obtain written informed consent and afterwards by phone by the investigator. At the beginning of the contact oral informed consent will also be obtained.

APPENDIX

Description of the procedures:

Conventional radiofrequency treatment of the genicular nerves is performed in an outpatient setting. Patients are not required to stop anticoagulation prior to procedure. During the procedure the patient is monitored using pulse oximetry. No sedation is administered so the patient is able to communicate and report the stimulation adequate. The patient is placed in a supine position on a fluoroscopy table with the index knee flexed 10-15° by placing a cushion in the popliteal fossa.

Description of the procedure of the diagnostic nerve block

The eligible patients underwent diagnostic genicular nerve blocks with local anesthetic, which were performed under ultrasound guidance. The targets included the SL, SM and IM genicular nerves which pass periosteal areas connecting the shaft of the femur to bilateral epicondyles and the shaft of the tibia to the medial epicondyle. Lidocaine (1 mL of 2%) was injected at each target site. Responses were recorded as positive if the participant experienced a decrease in numeric pain scores of at least 50%. Patients with a positive response were included in the RF procedures.

Description of the procedure of conventional radiofrequency ablation

The procedure is performed under sterile conditions. A 100 mm long, 22 G straight RF cannula/introducer with a probe/electrode with a 5 mm active tip is used for the procedure. No corticosteroids are injected to decrease the risk of complications such as systemic effects and infection. The superomedial, the superolateral and the inferomedial genicular nerve are targeted using a high frequency linear ultrasound. The inferolateral genicular nerve is not targeted because of its proximity to the common peroneal nerve with its motor branches.

Superomedial genicular nerve

The transducer is placed in a coronal orientation on the medial side of the proximal knee. After identifying the femoral medial epicondyle, the transducer is displaced proximally to image the junction between the epiphysis and diaphysis of the femur and the vastus medialis superficial to it, just anterior to the adductor tubercle. The skin and soft tissue are anesthetized with 1 ml lidocaine 2% at the estimated entry point. The superomedial genicular artery may or may not be seen between the deep fascia of the muscle and the femur at this level. If the superomedial genicular artery is visualised just above the bony cortex, the cannula tip is placed next to it using an cephalad to caudad 'in plane' approach. If the artery is not visualised, the cannula is advanced until contact is made with the bony cortex at the junction also using an cephalad to caudad 'in plane' approach. A RF electrode is introduced in the cannula. Sensory stimulation (50Hz) is applied and produced paresthesia at a threshold of less than 0,5 V. The absence of fasciculations below 1 V is observed after motor stimulation at 2 Hz, confirming sufficient distance to relevant motor branches. If no sensory stimulation threshold is obtained at this position, the transducer is rotated in a transverse view and the needle tip is redirect towards the middle of the femur until sensory threshold is reached.

Inferomedial genicular nerve

The transducer is placed in a coronal orientation on the medial side of the distal knee to visualize the junction of the tibial medial epiphysis and diaphysis, the inferomedial genicular artery and the medial collateral ligament. The skin and soft tissue are anesthetized with 1 ml lidocaine 2% at the estimated entry point. The inferomedial genicular artery may or may not be seen beneath the medial collateral ligament at the midpoint between the tibial medial epicondyle and the tibial insertion of the medial collateral ligament. If the inferomedial genicular artery is visualized just above the bony cortex, the cannula tip is placed next to it using an caudad to cephalad 'in plane' approach. If the artery is not visualized, the cannula is advanced until contact is made with the bony cortex at the junction also using an caudad tot cephalad 'in plane' approach. A RF electrode is introduced in the cannula. Sensory stimulation (50 Hz) is applied and produced paresthesia at a threshold of less than 0,5 V. The absence of fasciculations below 1 V is observed after motor stimulation at 2 Hz, confirming sufficient distance to relevant motor branches. If no sensory stimulation threshold is obtained at this position, the transducer is rotated in a transverse view and the needle tip is redirect towards the middle of the tibia until sensory threshold is reached.

Superolateral genicular nerve

The transducer is placed in a coronal orientation on the lateral side of the proximal knee. After identifying the femoral lateral epicondyle, the transducer is displaced proximally to image the junction between the epiphysis and diaphysis of the femur and the vastus lateralis superficial to it. The skin and soft tissue are anesthetized with 1 ml lidocaine 2% at the estimated entry point. The superolateral genicular artery may or may not be seen between the deep fascia of the muscle and the femur at this level. If the superolateral genicular artery is visualized just above the bony cortex, the cannula tip is placed next to it using an 'in plane' approach. If the artery is not visualized, the cannula is advanced until contact is made with the bony cortex at the junction also using an 'in plane' approach. A RF electrode is introduced in the cannula. Sensory stimulation (50 Hz) is applied and produced paresthesia at a threshold of less than 0,5 V. The absence of fasciculations below 1 V is observed after motor stimulation at 2 Hz, confirming sufficient distance to relevant motor branches. If no sensory stimulation threshold is obtained at this position, the transducer is rotated in a transverse view and the needle tip is redirect towards the middle of the femur until sensory threshold is reached.

If all three target nerves were identified 1 ml of lidocaine 2% is injected before the start of a RF treatment without a fluoroscopic control. A treatment of 70°C at the tip is applied during 90 seconds at each nerve. After the procedure, the patient is transferred to the recovery. After 30 minutes without any events, the patient is discharged at home. Home medication is continued postoperative. Patient is informed about potential transient increase in pain due to neuritis and alarm symptoms (fever, swelling, bleeding and motor weakness).
